5.2.5.2 Procedures

All procedures collected on the eCRF will be presented in a data listing.

5.2.6 Treatment Compliance and Extent of Exposure

5.2.6.1 Extent of Exposure

In general, subjects in each cohort at each dosing schedule received study drug in the range of 30 to 70 mg with 50 mg being the most common dose, as planned in the protocol. However, one subject from Cohort 1 and two subjects from Cohort 2 received 500 mg of study drug for each daily dose during their treatment period. In addition, dosing amount of another two subjects from Cohort 1 at Day 1 is missing because the site personnel inadvertently did not record the amount dosed after applying the study treatment on the subjects. Compared with other subjects, these overdosed or dose-missing subjects showed similar safety and activity profiles. Thus, they are still considered as protocol-eligible subjects.

The number of doses each subject received will be summarized as a continuous variable by cohort at each visit.

5.2.6.2 Treatment Compliance

Study treatment compliance will be defined as the actual number of doses a subject received divided by the planned number of doses, 5 (Cohort 1) or 3 (Cohort 2). Study treatment compliance will be summarized by cohort.

5.3 Data Analysis General Considerations

Both cohorts will be analyzed with the same statistical methods. Since this is not a dose regimen-randomized study, contrast between the 2 cohorts may be performed, but would mainly be noninferential, and consist of listings and descriptive statistics.

5.4 Activity Analyses

5.4.1 Primary Activity Analyses

The proportion of subjects with 100% clearance of all treated AK lesions at Day 57 will be considered to follow a binomial distribution. Based on the number of subjects who achieved 100% clearance at Day 57, the complete response rate and its corresponding 95% Clopper-Pearson Exact CI will be estimated in the Evaluable Set.

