9.7.1.6 Activity Analyses

AK lesion counts will be summarized by cohort at Day 1 (pretreatment) and at each subsequent timepoint for subjects in the Full Analysis Set and the Per-Protocol Set.

A 95% confidence interval (CI) for the complete clearance (response rate) at Day 57 will be estimated by cohort in the Evaluable Set.

Recurrence rates for all subjects who achieved complete clearance at Day 57 will be estimated by timepoint and cohort in the Evaluable Set.

A 95% CI for the sustained response rate at 12 months post-Day 57 will be estimated by cohort in the Evaluable Set.

Both cohorts will be analyzed with the same statistical methods. Since this is not a dose regimen randomized study, any contrast between the 2 cohorts will mainly be noninferential and consist of listings, graphs, and descriptive statistics.

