5 STATISTICAL METHODS

Statistical analyses will be reported using summary tables, graphs and data listings. In general, continuous variables will be summarized with mean, standard deviation (SD), median, minimum, and maximum. Categorical variables will be summarized with counts and percentage of subjects in corresponding categories.

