5.2 Study Subjects

5.2.1 Definitions of Analysis Sets

- Per-Protocol Set: the group of protocol-eligible subjects who receive 5 days (Cohort 1) or 3 days (Cohort 2) of study treatment and complete at least one scheduled post-treatment AK lesion evaluation
- Evaluable Set: the group of protocol-eligible subjects who receive 5 days (Cohort 1) or 3 days (Cohort 2) of treatment and complete Day 1 and Day 57 AK lesion evaluations
- Safety Analysis/Full Analysis Set: the group of subjects who receive at least one dose of study treatment
- Recurrence Follow-up Set: the group of subjects who achieve complete clearance at Day 57

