5.2.2 Subject Disposition

For screen failure subjects, a listing will be provided to present their screen failure reasons.

The number of subjects in each analysis set (Safety/Full Analysis, Per-Protocol, Evaluable, and Recurrence Follow-up) will be tabulated by cohort.

For the Safety/Full Analysis Set, subject disposition will be summarized by cohort for:

- Subjects dosed
- Subjects who completed the Day 57 visit
- Subjects who achieved 100% AK clearance at the Day 57 visit
- Subjects who discontinued before the Day 57 visit and their primary reason for discontinuation

In addition, the number of subjects dosed and the number of subjects who completed the Day 57 visit will be summarized by study site and cohort.

A listing of those subjects who discontinued before the Day 57 visit and the associated reasons will be presented.

For the Recurrence Follow-up Set, the recorded discontinuation reasons will be reviewed and subjects who discontinued early due to AK recurrence will be assigned “AK Recurrence” as the new primary reason for discontinuation.

Subject disposition will be summarized by cohort for:

- Subjects who entered the Recurrence Follow-up Period
- Subjects who completed the Recurrence Follow-up Period
- Subjects who discontinued during the Recurrence Follow-up Period and their primary reason for discontinuation

Subjects who discontinued during the Recurrence Follow-up Period will also be listed.

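### Clearance rates have a confidence interval only in the Evaluable Set, and the protocol's Full Analysis Set lesion-count summary is dropped without being listed as a change

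*SAP*

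**What the plan says.** **Complete and partial clearance.** SAP 5.4.1 states that "the complete response rate and its corresponding 95% Clopper-Pearson Exact CI will be estimated in the Evaluable Set". Section 5.4.3 applies the same analysis to partial clearance (at least 75%). Protocol 9.7.1.6 also placed the complete response interval in the Evaluable Set: "at Day 57 will be estimated by cohort in the Evaluable Set".

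**Lesion counts.** SAP 5.4.2 summarises counts and changes from baseline by visit in the Per-Protocol Set only. Protocol 9.7.1.6 planned them "at each subsequent timepoint for subjects in the Full Analysis Set and the Per-Protocol Set".

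**The sets (SAP 5.2.1).** Both activity sets take protocol-eligible subjects who received all 5 or 3 days of treatment. The Evaluable Set adds "of treatment and complete Day 1 and Day 57 AK lesion evaluations"; the Per-Protocol Set adds "of study treatment and complete at least one scheduled post-treatment AK lesion evaluation". The Full Analysis Set needs only one dose.

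**What the Full Analysis Set still receives.** The disposition summary in SAP 5.2.2 includes "Subjects who achieved 100% AK clearance at the Day 57 visit", and SAP 5 sets the general rule that "Categorical variables will be summarized with counts and percentage of subjects in corresponding categories". SAP 5.2.4 adds the baseline lesion count.

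**Declared changes.** SAP 7 lists four: the Evaluable Set definition, the new Recurrence Follow-up Set, the recoding of discontinuations as AK recurrence, and the Kaplan-Meier method. None concerns the Full Analysis Set. SAP 3 says the SAP replaces the protocol's statistical section, so the omission takes effect.

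**The concern.** Leaving the Evaluable Set can be related to outcome. Protocol 9.5.1.5.8 foresees study treatment being interrupted or stopped for a local skin reaction, and 9.4.7.3 withdraws subjects who start topical AK therapy on the treatment area. If excluded subjects clear less often, the evaluable rate overstates activity among everyone treated. In an open-label, uncontrolled study that also contrasts two regimens, a reader will want to know whether the rates hold in all treated subjects.

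Two further features make an all-treated figure more useful:

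- Protocol 9.7.1.2 does not require eligibility for the Evaluable Set. SAP 5.2.1 adds it, and Section 7 mentions only the lesion-evaluation part of the redefinition.
- SAP 5.2.6.1 keeps subjects with deviating or unrecorded dose amounts as protocol-eligible partly because their activity looked similar to that of others. Set membership was therefore judged with outcome data in view.

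The lesion-count loss is narrower. Eligible, fully dosed subjects with one post-treatment count remain in the Per-Protocol Set, so it is mainly incompletely dosed and ineligible subjects who disappear. The recurrence analyses use a different set and are outside this point.

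**Working it through.** **The plan's own figures (SAP 4; Protocol 9.1).** Inputs: 60 evaluable per cohort, 35% response against 20%, two-sided 0.05, 80% power, under 25% dropout, about 80 enrolled.

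- Enrolment: 60 / (1 − 0.25) = 80, which agrees.
- Power by normal approximation: Φ[(0.15·√60 − 1.96·√(0.2·0.8)) / √(0.35·0.65)] = 78.6%, close to 80%. The exact rule matching the planned interval (at least 19 of 60) gives 74.8%. This point does not depend on either figure.
- Exact interval at 21/60: 23.1% to 48.4%, half-width 12.6 points, consistent with the stated half-width below 15 and a lower limit above 20%.

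**Method for the illustration.** The Clopper-Pearson limits for x of n are the 0.025 quantile of Beta(x, n − x + 1) and the 0.975 quantile of Beta(x + 1, n − x). Actual attrition is not in the documents, so a range is used. Treated N = 60 / (1 − attrition), rounded: 60/0.95 = 63; 60/0.90 = 67; 60/0.75 = 80. The 80 are enrolled subjects, so the treated number may be smaller.

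**Complete response, 21 evaluable responders, no excluded subject clear:**

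| Denominator | Rate | Exact 95% CI |
|---|---|---|
| 60 (Evaluable) | 35.0% | 23.1 to 48.4 |
| 63 (5% attrition) | 33.3% | 22.0 to 46.3 |
| 67 (10%) | 31.3% | 20.6 to 43.8 |
| 68 (8 excluded) | 30.9% | 20.2 to 43.3 |
| 69 (9 excluded) | 30.4% | 19.9 to 42.7 |
| 80 (25% ceiling) | 26.3% | 17.0 to 37.3 |

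The shift is 35.0 − 33.3 = 1.7 points at 5% attrition, 35.0 − 31.3 = 3.7 at 10%, and 35.0 − 26.25 = 8.75 at the ceiling. The lower limit passes below 20% at the ninth exclusion. That 20% is the sample-size reference value, not a success rule.

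**Bias absent or reversed, 7 excluded.** If 2 of them are clear: 23/67 = 34.3%, about no bias. If 3 are clear: 24/67 = 35.8% (24.5 to 48.5), above the evaluable rate. This can happen because a subject who missed a dose but is clear at Day 57 is also excluded.

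**Partial clearance.** There is no planning value, so an evaluable rate of 50% to 70% (30/60 to 42/60) is assumed, again with no excluded subject responding:

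| Attrition | Evaluable 50% | Evaluable 70% |
|---|---|---|
| 10% (N = 67) | 44.8% (32.6 to 57.4) | 62.7% (50.0 to 74.2) |
| 25% (N = 80) | 37.5% (26.9 to 49.0) | 52.5% (41.0 to 63.8) |

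**Planned outputs by analysis set:**

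| Output | Protocol 9.7.1.6 | SAP | Listed in SAP 7 |
|---|---|---|---|
| Complete response CI | Evaluable | Evaluable | Unchanged set; its definition is listed in part |
| Lesion counts by visit | Full Analysis and Per-Protocol | Per-Protocol | No |
| Partial clearance CI | Not planned | Evaluable | No |

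**The case against.** The strongest reply is that little is lost. The protocol itself chose the Evaluable Set, the study is a Phase 2a trial without a control group, cohort contrasts are mainly non-inferential, and no decision rests on a Full Analysis Set interval. For complete response the disposition table gives the numerator and denominator by cohort. If the percentage is taken over dosed subjects, those with no Day 57 count are in effect non-responders, and anyone can compute the interval. What disappears from the lesion-count table is probably a small group, since site staff apply every dose over 5 or 3 days. Protocol 9.7.5 also promises that revisions will be described in the study report.

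Much of this stands. It rules out calling the primary analysis wrong, and it makes the complete response gap a matter of a missing interval and an unstated rule.

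It does not cover the rest. Partial clearance has no planned overall all-treated figure. The only explicit Full Analysis Set lesion-count summary is at baseline. The subgroup analyses in SAP 5.4.5 name no set and give no overall estimate. The discontinuation reasons, and the commitment in SAP 5.2.6.2 that "Study treatment compliance will be summarized by cohort", help a reader judge why subjects were excluded, but they estimate no activity. A later promise to describe revisions does not make the Section 7 list complete.

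**Conclusion.** The point holds and should be fixed. The removal of the Full Analysis Set lesion-count summary is a plain, unlisted departure from the protocol. The lack of an all-treated clearance rate with its uncertainty is a gap in the plan, not a departure from the protocol.

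The effect on complete response is small against the interval width at 5% to 10% attrition (1.7 to 3.7 points) and material at the planning ceiling (8.75 points). Those figures assume the planned 35% in the Evaluable Set and no clearance among excluded subjects. With some clearance among them, the bias may vanish or change sign. The partial clearance figures also rest on an assumed evaluable rate of 50% to 70%.

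**What to change.** 1. Keep the Evaluable Set as primary and add no success rule.
2. In SAP 5.4.1, add a supportive complete response rate with an exact 95% interval in the Full Analysis Set, by cohort, shown beside the Evaluable Set result. State the rule: no Day 57 lesion count means non-responder; subjects who missed doses but attended contribute their observed Day 57 count.
3. Do the same for partial clearance in 5.4.3.
4. Restore the Full Analysis Set lesion-count table from Protocol 9.7.1.6. If it is not restored, list its removal in Section 7.

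The cost is a few tables from data already collected and a short SAP addition; the primary analysis does not change. The downside is that the all-treated rate may come out lower than the evaluable one, and counting missing as non-response is conservative if some dropouts would have cleared.

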5.4.2 Secondary Activity Analyses

The number of AK lesions at the Screening, Day 1, Day 8, Day 15, Day 29, and Day 57 visits and actual/percentage lesion number change from baseline will be summarized by cohort at each visit in the Per-Protocol Set. Baseline values are defined as the assessments at Day 1.

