3 INTRODUCTION

This Statistical Analysis Plan (SAP) is based on the protocol for study KX01-AK-002 Amendment 2, v3.0, dated 26SEP2016. This SAP supersedes the statistical section of the protocol and provides data analysis details for the activity and safety data analysis in the clinical study report (CSR). It does not include information regarding the pharmacokinetic (PK) analysis of the study drug, KX2-391 Ointment 1.0%; that information is provided separately.

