5.1.2 Secondary Endpoints

- Activity: Reduction in lesion counts during Days 1-57
- Safety: Evaluation of adverse events (AEs), local skin reactions (LSRs) and clinical laboratory data; the results of other safety assessments (vital signs, physical examinations, ECGs) will also be evaluated

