7 CHANGES IN THE PLANNED ANALYSES

Definition of the Evaluable Set is updated to include Day 1 and Day 57 AK lesion evaluations only.

The Recurrence Follow-up Set is defined in this document to analyze data collected during the Recurrence Follow-up Period.

AK recurrence is not listed as a discontinuation event on CRF. The Sponsor reviewed all collected disposition event details and recategorized the subjects who discontinued due to AK recurrence in the Recurrence Follow-up Period into a new category of primary reason for discontinuation - "AK recurrence" (See Section 12.3).

The recurrence rates and the sustained response rate will be estimated with a Kaplan-Meier method to consider censored subjects who discontinued due to non-AK recurrence reasons.

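### SAP 5.4.2 summarises lesion counts and change in the Per-Protocol Set only; the Full Analysis Set summary planned in the protocol is gone, and SAP Section 7 does not list the change

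*SAP*

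**What the plan says.** SAP 5.1.2 gives the secondary activity endpoint as "Activity: Reduction in lesion counts during Days 1-57". For its analysis, SAP 5.4.2 states that the actual and percentage "lesion number change from baseline will be summarized by cohort at each visit in the Per-Protocol Set". The counts themselves are summarised in the same sentence and the same set.

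Protocol v3.0, section 9.7.1.6, plans lesion counts by cohort at Day 1 and "at each subsequent timepoint for subjects in the Full Analysis Set and the Per-Protocol Set". The synopsis of that version has the same rule.

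The two sets differ in SAP 5.2.1. The first is "Safety Analysis/Full Analysis Set: the group of subjects who receive at least one dose of study treatment". The Per-Protocol Set is "the group of protocol-eligible subjects who receive 5 days (Cohort 1) or 3 days (Cohort 2) of study treatment" who also "complete at least one scheduled post-treatment AK lesion evaluation".

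On precedence, SAP Section 3 reads: "This SAP supersedes the statistical section of the protocol and provides data analysis details for the activity and safety data analysis".

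**The concern.** The protocol promised a view of lesion counts in everyone treated, beside a view in those treated as planned. The SAP keeps only the second. Anyone who stopped dosing early, for example because of a skin reaction, and anyone treated but found ineligible, drops out of the secondary activity endpoint. If those subjects did worse than the rest, the reported reduction is too favourable. A reader of the report would have no companion table from which to judge this.

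The endpoint also feeds a secondary objective, the contrast of 5-day with 3-day treatment. Entry to the Per-Protocol Set requires 5 days of treatment in one cohort and 3 in the other, so the filter is not the same for both regimens.

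Finally, a set named in the protocol has disappeared without being declared, in an open-label study where activity is tabulated after about every 20 subjects (SAP Section 6).

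**Working it through.** The plan states no figure on this point. Its sample-size figures concern the Day 57 complete response rate and do not depend on which set carries the lesion-count summary. The check is therefore textual, followed by an illustration of size.

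**Step 1. Sets named for lesion counts over visits**

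| Source | Full Analysis Set | Per-Protocol Set |
|---|---|---|
| Protocol v3.0, synopsis | yes | yes |
| Protocol v3.0, 9.7.1.6 | yes | yes |
| SAP 5.4.2 | no | yes |

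The SAP says it is based on protocol v3.0, so this is a difference from current text, not from a superseded version.

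**Step 2. Is the change declared?** SAP Section 7 lists four changes:
- the Evaluable Set ("Definition of the Evaluable Set is updated to include Day 1 and Day 57 AK lesion evaluations only");
- the new Recurrence Follow-up Set;
- the recategorised reason for discontinuation;
- Kaplan-Meier estimation of recurrence and sustained response.

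The set for lesion counts is not among them.

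**Step 3. Does another output fill the gap?**
- SAP 5.4.1 uses the Evaluable Set for complete clearance, and 5.4.3 follows it for partial clearance. That set also requires eligibility and the full course.
- SAP 5.2.2 counts, in the Full Analysis Set, subjects with 100% clearance at Day 57. This is a responder count, not a reduction over visits.
- SAP 5.2.4 tabulates baseline lesion count in the Full Analysis Set, with nothing after baseline.

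Every Day 1-57 activity analysis in SAP 5.4.1 to 5.4.3 is thus limited to eligible subjects who received the full course.

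**Step 4. Who is left out?** A treated subject is outside the Per-Protocol Set if ineligible, if the course was incomplete, or if there is no post-treatment lesion evaluation. The third group has no change to report in either set. Only the first two can move a Full Analysis Set mean, and only through counts actually taken.

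**Step 5. Illustration of size.** At a given visit let N be the treated subjects with a count, k those of them outside the Per-Protocol Set, m the mean percentage reduction inside that set and r the mean outside it.

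All-treated mean = [(N − k) × m + k × r] / N

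Gap = m − all-treated mean = (k / N) × (m − r)

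N = 80 is the planned enrolment per cohort, taken here as if all had a count. The values m = 80%, r = 0% to 40% and k = 4 or 8 are assumptions; the documents give none of them.

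| k | r | All-treated mean | Gap (points) |
|---|---|---|---|
| 4 | 40% | (76 × 80 + 4 × 40) / 80 = 78% | 2 |
| 4 | 0% | (76 × 80) / 80 = 76% | 4 |
| 8 | 40% | (72 × 80 + 8 × 40) / 80 = 76% | 4 |
| 8 | 0% | (72 × 80) / 80 = 72% | 8 |

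If r equals m the gap is zero. If r exceeds m the sign reverses.

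**The case against.** The case for leaving the SAP alone is that little depends on this. The endpoint is descriptive, in a nonrandomised open-label Phase 2a study. Staff apply every dose at the site over 3 or 5 days, so few subjects may miss a dose. The Per-Protocol Set is not tightly drawn either: SAP 5.2.6.1 keeps subjects with departures in the recorded dose amount as eligible. All of this stands and limits the importance of the point. It does not restore the missing summary, and that same section justifies eligibility partly by observed activity, a judgement on which the Full Analysis Set does not depend.

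Protocol 9.7.5 lets revisions be described in the clinical study report, so Section 7 is not the only place to declare one. That is correct, but Section 7 exists for this purpose and already lists comparable changes.

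A Full Analysis Set table may also add less than hoped. Under protocol 9.5.4, subjects who withdraw from treatment are only encouraged to complete early-termination assessments. The SAP states no rule for missing lesion counts; LOCF appears only in its abbreviation list. This stands, and is why the illustration covers only subjects with a count.

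Several stronger readings are tempting but unsupported:
- **That up to 25% of subjects could be outside the Per-Protocol Set.** The 25% dropout ceiling links about 80 enrolled to about 60 evaluable (60 / (1 − 0.25) = 80). Someone fully dosed and counted at Day 8 who then leaves is not evaluable but stays in the Per-Protocol Set.
- **That the 5-day cohort is flattered more.** Nothing in the documents shows early stopping by cohort.
- **That no table of any kind will show this.** Mock tables are standalone documents (SAP Section 11) and are not available; the statement is limited to the SAP text.
- **That the cohort contrast must rest on the Full Analysis Set.** Neither document names a set for it, and SAP 5.3 calls any contrast mainly noninferential.
- **That the protocol promised change from baseline in both sets.** Its analysis section promises counts; change and percentage change come from the SAP.

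**Conclusion.** The point holds as an undeclared departure of the SAP from the current protocol, with a plausible but unquantified effect on how the secondary activity endpoint reads. On the assumed inputs the effect is 2 to 8 percentage points in the mean reduction. It rests on excluded subjects having counts and doing worse than those retained, neither of which the documents establish. The direction between cohorts cannot be determined. The primary analysis is unaffected. The change is worth making because it is cheap and returns the plan to what the protocol set out, not because a wrong result has been shown.

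**What to change.** In SAP 5.4.2, summarise lesion counts, change and percentage change by visit and cohort in both the Full Analysis Set and the Per-Protocol Set. Use observed data and print n at each visit, so that the reader sees how many treated subjects contribute. Change and percentage change belong in both tables because the endpoint is a reduction.

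List any departure from protocol 9.7.1.6 that remains in SAP Section 7. If the sponsor prefers the Per-Protocol Set alone, state that there with the reason.

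The cost is one amended sentence and one repeated descriptive table from data already collected. Sample size, alpha and power do not change.
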